8.4.2 Unanticipated Problem Reporting

The investigator will report unanticipated problems (UPs) to the reviewing Institutional Review Board (IRB) and to the Data Management/lead principal investigator (PI). The UP report will include the following information:

- Protocol identifying information: protocol title and number, PI's name, and the IRB project number.
- A detailed description of the event, incident, experience, or outcome.
- An explanation of the basis for determining that the event, incident, experience, or outcome represents an UP.
- A description of any changes to the protocol or other corrective actions that have been taken or are proposed in response to the UP.

To satisfy the requirement for prompt reporting, UPs will be reported using the following timeline:

- UPs that are serious adverse events (SAEs) will be reported to CRO study team within 24 hours
- CRO study team will review and request additional information immediately and report the information to the IRB and to the DSMB/study Sponsor within 24 hours of the CRO study team becoming aware of the event.
- Any other UP will be reported to the IRB and to the DSMB/study Sponsor within 48 hours of the investigator becoming aware of the problem.
- All UPs should be reported to appropriate institutional officials (as required by an institution's written reporting procedures), the supporting agency head (or designee), after the IRB's receipt of the report of the problem from the investigator.

8.4.3 Reporting Unanticipated Problems to Parents/Legal Guardians

Not applicable.

9 Statistical Considerations

9.1 Statistical Hypothesis

This study was designed to show that high dose phenobarbital (40 mg/kg) is more effective than low dose phenobarbital (20 mg/kg) following single dose administration in terms of study's primary endpoint ([Section 3.2.1](#)). Specifically, the following primary statistical hypotheses will be tested.

Null hypothesis H_0 : there is no difference between treatments in the proportion of participants having a primary efficacy endpoint.

Alternative hypothesis H_a : The proportions of participants having a primary efficacy endpoint are different between the two treatment groups.

9.2 Sample Size Determination

Literature supports that lower loading doses of phenobarbital achieve seizure control in approximately 30 to 60% of treated neonates, with higher loading doses achieving seizure control up to 85% (19, 20, 23, 24). Based on 70% and 50% of study participants achieving seizure control in high dose and low, respectively, an effect size of 20%, an alpha of 0.05 and 80% power, it is estimated that the number of completed study participants required will be 93 study participants in each group (total 186). With approximately, 5% dropout or unevaluable study participant, the minimum required for randomization will be 196.

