4.4 End of Study Definition

A study participant is considered to have completed the study if he or she has completed all phases of the study including the last scheduled procedure prior to discharge shown in the Schedule of Activities (SoA).

The end of the study is defined as completion of the last procedure shown in the SoA in the trial for the last enrolled study participant.

5 Study Population

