5.5 Strategies for Recruitment and Retention

5.5.1 Target Study Sample Size

Literature supports that lower loading doses of phenobarbital achieve seizure control in approximately 30 to 60% of treated neonates, with higher loading doses achieving seizure control up to 85% (19, 20, 23, 24). Based on 70% and 50% of study participants would achieve seizure control in high dose and low, respectively, an effect size of 20%, an alpha of 0.05 and 80% power, it is estimated that the number of completed study participants required will be 93 study participants in each group (total 186). With approximately, 5% dropout and or non-evaluable study participants, the minimum required for randomization will be 196. A screen failure rate of approximately 60% is anticipated. A total of 490 study participants would be enrolled.

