9.3 Populations For Analyses

1. *Intention-to-treat (ITT) population*: Study participant population consists of all randomized study participants with valid informed consent.
2. *Per-protocol (PP) population*: A Subset of the ITT population. Study participants with major protocol deviations will be excluded from PP population. Major protocol deviations will be defined in the Statistical Analysis Plan (SAP).
3. *Safety population*: A subset of the ITT population, consisting of all randomized study participants who receive at least one dose or partial dose of study drug.
4. *Pharmacokinetic (PK) population*: Study participants that received at least 1 dose from the same study arm (as per randomization or per error) are included in this population group.

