9.4.2 Analysis of the Primary Efficacy Endpoint(s)

The primary endpoint will be summarized by number and percent of participants with events and compared by a log binomial model (a generalized linear model [GLM]) that includes treatment as a study variable, which will generate risk ratio (RR) together with their 95% CIs of having a primary outcome between high dose and low dose groups. A study participant who is withdrawn from the study within the first 24 hours after treatment will be considered not to have achieved the primary endpoint. Treatment of such dropouts with respect to other endpoints will be specified in the SAP.

In addition, covariate adjustment will be performed by GLM model with treatment as a study variable and, gender, gestational age, birth weight, apgar scores, liver function tests, seizure etiology, therapeutic hypothermia and pre-treatment seizure burden as covariates. From this

model, adjusted RR together with their 95% confidence interval will be derived. Imputation for these baseline missing covariates will be carried out for adjusted analysis.

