3.6. Sample Size

Literature supports that lower loading doses of phenobarbital achieve seizure control in approximately 30 to 60% of treated neonates, with higher loading doses achieving seizure control up to 85%. Based on an effect size of 20% (from 50% in the low dose group to 70% in the high dose group), an alpha of 0.05 and 80% power, it is estimated that the number of completed subjects required will be 93 subjects in each group (total 186). With approximately, 5% dropout resulting in non-evaluable primary outcome, the minimum required for randomization will be 196.

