5.5.2. Primary outcome

Randomised subjects with missing responses will be treated as treatment failures

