7.1. Primary Outcome Analysis**7.1.1. Primary analysis**

The primary outcome in this trial is whether a neonate requires additional seizure treatment after the first dose of phenobarbital during the first 24 hours after treatment, which will be summarized by percent of neonates who do not require additional seizure treatment after the first dose of phenobarbital during the first 24 hours after treatment. The primary analysis will be based on the ITT as defined above.

The primary endpoint will be summarized by number and percent of participants with events by treatment and overall.

The primary hypothesis to be tested is $H_0: \pi_1 - \pi_2 = 0$ versus $H_1: \pi_1 - \pi_2 \neq 0$, where π_1 and π_2 are rates of primary outcome for high dose and low dose group, respectively. The primary efficacy variable will be analyzed using generalized linear model (GLM) with treatment as a study variable, HIE (presence or absence) and seizure burden (high or low) as covariates. Rate difference (RD) together with its 95% confidence interval (CI) will be derived with binomial distribution and identify link function in the GLM model. The estimated risk ratio/relative risk (RR) and its 95% CI will also be provided with binomial distribution and log link function instead.

The above identity-binomial GLM model may not converge when all covariates are introduced into the model simultaneously. To avoid non-convergence issue, we will first calculate a propensity score with treatment as the dependent variable (1 for treatment A and 0 for treatment B) and all covariates listed above as independent variables through a logistic regression model, and then include the calculated propensity score (continuous variable) as a covariate in the identity-binomial GLM model.

CONFIDENTIAL

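### The step from 186 to 196 assumes non-evaluable neonates leave the analysis, but the primary analysis keeps them as failures; if 70%/50% are completer rates, power is about 77%, not 80%

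*Protocol*

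**What the plan says.** The sample-size statement appears three times with the same figures: 70% against 50%, alpha 0.05, 80% power, 93 completed neonates per arm, 186 in total, 196 to be randomised. The descriptions of the 5% differ slightly.

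- Protocol 9.2: "With approximately, 5% dropout or unevaluable study participant, the minimum required for randomization will be 196".
- Protocol 5.5.1: "With approximately, 5% dropout and or non-evaluable study participants, the minimum required for randomization will be 196".
- SAP 3.6, which ties the 5% to the endpoint itself: "With approximately, 5% dropout resulting in non-evaluable primary outcome, the minimum required for randomization will be 196".

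The analysis rules are these.

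- Analysis set, SAP 7.1.1: "The primary analysis will be based on the ITT as defined above". Protocol 9.3 defines ITT: "Study participant population consists of all randomized study participants with valid informed consent". SAP 4.1 gives the same definition.
- Withdrawals, Protocol 9.4.2: a neonate "withdrawn from the study within the first 24 hours after treatment will be considered not to have achieved the primary endpoint".
- Missing primary outcome, SAP 5.5.2: "Randomised subjects with missing responses will be treated as treatment failures".

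**The concern.** Dividing 186 by 0.95 is the usual allowance when some participants contribute nothing to the analysis: randomise more so that the required number is left. Here nobody is removed. A neonate whose 24-hour outcome cannot be evaluated stays in the ITT denominator and counts as a failure. The extra 10 neonates therefore do not replace lost observations. They enlarge the sample, while the failure coding lowers both response rates and narrows the difference between them.

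The primary comparison is the only confirmatory test in the plan, because SAP 5.6 treats the secondary and additional analyses as exploratory. A reader cannot tell from the text what power that comparison has. The answer turns on whether 70%/50% are rates among completers or among all randomised neonates, which neither document states. Asking for 93 completed neonates per arm points to completers but does not settle it.

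**Working it through.** **Inputs.** Rates 70% and 50%, alpha 0.05, power 80%, 93 per arm, 5% and 196: Protocol 9.2 and SAP 3.6. Two-sided test: Protocol 9.1 and SAP 7.1.1. Allocation 1:1: Protocol 4.1, so 98 per arm. Neither document names the formula. The pooled-variance normal formula without continuity correction is inferred because it reproduces 93.

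**Step 1: reproduce the plan's figures.** With p̄ = (p1 + p2)/2,

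n per arm = [1.960·√(2p̄(1−p̄)) + 0.842·√(p1(1−p1) + p2(1−p2))]² / (p1 − p2)²

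For 0.70 and 0.50, p̄ = 0.60, and the two terms are 1.3579 and 0.5708:

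n = (1.3579 + 0.5708)² / 0.20² = 92.999, so 93 per arm and 186 in total.

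Dropout step: 186 / 0.95 = 195.8, so 196. Both figures reproduce.

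**Step 2: rates under the rule the analysis uses.** Let q be the share in each arm whose outcome is coded as failure only because of withdrawal or missing data. If 70%/50% are completer rates, the ITT rates are 0.70(1−q) and 0.50(1−q). At q = 0.05 they are 0.665 and 0.475, a difference of 19 points instead of 20.

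**Step 3: power at 98 per arm.**

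power = Φ{ [|p1−p2|·√n − 1.960·√(2p̄(1−p̄))] / √(p1(1−p1) + p2(1−p2)) }

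- q = 0 (also the all-randomised reading): (1.9799 − 1.3579)/0.6782 = 0.917, power 82.0%.
- q = 0.05: (1.8809 − 1.3723)/0.6871 = 0.740, power 77.0%.

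Exact enumeration of the pooled z-test at 66.5% against 47.5% gives 77.5%. The unpooled normal formula gives 78.2%.

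**Step 4: how far the result depends on q.**

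| Failure-coded share, each arm | Expected rates | Power, 98 per arm |
|---|---|---|
| 0% | 70.0% / 50.0% | 82.0% |
| 2% | 68.6% / 49.0% | 80.1% |
| 3% | 67.9% / 48.5% | 79.1% |
| 4% | 67.2% / 48.0% | 78.1% |
| 5% | 66.5% / 47.5% | 77.0% |
| 8% | 64.4% / 46.0% | 73.9% |
| 10% | 63.0% / 45.0% | 71.8% |

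Power equals 80% at q = 2.1%.

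**Step 5: unequal shares.** The documents give no split between arms, so an equal split is an assumption. With 6% in the high-dose arm and 4% in the low-dose arm the rates are 65.8% and 48.0%, and power is 71.4%. With 4% and 6% the rates are 67.2% and 47.0%, and power is 82.0%.

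**Step 6: scale only.** Holding 80% at 66.5% against 47.5% would need (1.3723 + 0.5783)² / 0.19² = 105.4, so 106 per arm or 212 in total.

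**The case against.** Several points on the other side are fair.

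- **No figure is miscalculated.** 93, 186 and 196 are right on their own terms. This stands: the fault is that the dropout step and the missing-data rule do not fit together.
- **The completer reading is not established.** The text speaks of study participants achieving seizure control and cites literature on treated neonates. This also stands, so 77% is conditional. But on the all-randomised reading the inflation has no purpose and power is 82%, so the sample-size text needs correcting either way.
- **Some of the 5% may have a known outcome.** Protocol 4.4 says: "A study participant is considered to have completed the study if he or she has completed all phases of the study". A neonate who leaves after 24 hours is then not a completer but has a primary outcome. That is possible under the protocol's wording, and the 2% to 4% rows show the effect. SAP 3.6 limits its 5% to dropout that makes the primary outcome non-evaluable.
- **The loss is small beside the planning uncertainty.** At 98 per arm, a low-dose rate of 51% instead of 50% gives 78.1%, and a high-dose rate of 69% gives 77.8%. True, and it limits the weight of the point. It does not justify a power statement built on a rule that is not applied.
- **The planned model is adjusted, and 196 is a minimum.** SAP 7.1.1 adjusts for HIE and seizure burden. Any gain from that cannot be quantified from the documents. Randomising more than 196 would raise power, but no larger number is stated.

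**Conclusion.** The concern holds. The stated 80% depends on neonates leaving an analysis that by definition keeps them, and this is so under either reading of the assumed rates. If 70%/50% are completer rates and 5% in each arm are coded as failures, power at 98 per arm is about 77%, roughly 3 points below the stated value. If they are all-randomised rates, it is about 82%, roughly 2 points above.

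The 77% assumes an equal 5% share in each arm, unrelated to whether the neonate would have responded, and an unadjusted comparison. It moves noticeably if the share is smaller, larger or unequal. The mismatch between the two rules is certain; the exact power is not. Estimation is unaffected: the ITT set, the failure coding and the model stay as they are. What is wrong is the power statement and its reasoning, and it should be corrected.

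**What to change.** In Protocol 5.5.1 and 9.2 and SAP 3.6, state that all 196 randomised neonates enter the primary analysis and that those without an evaluable 24-hour outcome count as failures. Then choose one of two statements.

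- (a) 70%/50% are completer rates. With 5% coded as failures in each arm, the expected rates are 66.5% and 47.5%, and power at 98 per arm is about 77%. Show power over a range of failure-coded shares, since 5% is only approximate.
- (b) 70%/50% are rates among all randomised neonates, failures included. Remove the dropout rationale and state power of about 82% at 98 per arm.

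The cost is wording only, with no added patients and no change to the analysis. Stated power becomes about 3 points less favourable under (a) or about 2 points more favourable under (b).

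A separate clarification, on which the verdict does not depend: Protocol 4.1 (screen failure when study drug is not given within two hours), 5.4 (screen failures are not randomised) and 7.2 (randomised but undosed neonates may be replaced) need to be reconciled with the ITT definition. Any neonate already randomised should stay in the ITT set, with a replacement counted as additional.

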9.3 Populations For Analyses

1. *Intention-to-treat (ITT) population*: Study participant population consists of all randomized study participants with valid informed consent.
2. *Per-protocol (PP) population*: A Subset of the ITT population. Study participants with major protocol deviations will be excluded from PP population. Major protocol deviations will be defined in the Statistical Analysis Plan (SAP).
3. *Safety population*: A subset of the ITT population, consisting of all randomized study participants who receive at least one dose or partial dose of study drug.
4. *Pharmacokinetic (PK) population*: Study participants that received at least 1 dose from the same study arm (as per randomization or per error) are included in this population group.

9.4 Statistical Analyses

9.4.1 General Approach

Please refer to the SAP for specific details.

9.4.2 Analysis of the Primary Efficacy Endpoint(s)

The primary endpoint will be summarized by number and percent of participants with events and compared by a log binomial model (a generalized linear model [GLM]) that includes treatment as a study variable, which will generate risk ratio (RR) together with their 95% CIs of having a primary outcome between high dose and low dose groups. A study participant who is withdrawn from the study within the first 24 hours after treatment will be considered not to have achieved the primary endpoint. Treatment of such dropouts with respect to other endpoints will be specified in the SAP.

In addition, covariate adjustment will be performed by GLM model with treatment as a study variable and, gender, gestational age, birth weight, apgar scores, liver function tests, seizure etiology, therapeutic hypothermia and pre-treatment seizure burden as covariates. From this

model, adjusted RR together with their 95% confidence interval will be derived. Imputation for these baseline missing covariates will be carried out for adjusted analysis.

9.4.3 Analysis of the Secondary Endpoint(s)

The secondary outcomes will be analyzed similarly as the primary endpoint analysis using a GLM. For GLM analysis of a continuous endpoint such as quality of life, normal distribution and identity link functions will be used; for GLM analysis of a binary outcome (such as having a primary endpoint), binomial distribution and log link functions will be used.

For the analysis of time-to-event outcome, the Kaplan-Meier curves will be presented and compared by the log rank test by treatment group and hazard ratio and its 95% confidence interval will be calculated using Cox regression model with the treatment arm as the study variable.

The secondary binary outcomes with repeated measurements at different time points will be summarized using number (%) of events at each time point and analyzed using a generalized linear mixed model (GLMMIX) model, in which treatment, time, interaction between treatment and time as fixed effects and participant as cluster effect. Exchangeable covariance structure will be used. The odds ratio together with their 95%CIs at each time point will be derived.

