5.3. Planned Covariates

Covariate analyses will be performed on the primary outcome on the ITT population. The prespecified covariates in this study will be:

Stratification factors

- Presence or absence of HIE
- High or low seizure burden

Baseline values

- Gender (binary)
- Gestational age (continuous)
- birth weight (continuous)
- Apgar scores (continuous)
- Liver function tests (Total Protein, Albumin, Bilirubin, ALP, AST, ALT) (continuous)
- Seizure etiology (binary)
- pre-treatment seizure burden (continuous)

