7.2.1. Analysis of binary outcomes

Binary outcome with single measurement will be summarised by number (%) of participants with event by treatment group and analysed in a similar way as the primary endpoint by means of GLM model. The point estimate of RD and its two-sided 95% CI between high dose and low dose will be estimated. If RD cannot be estimated, RR will be estimated.

The secondary binary outcomes with repeated measurements at different time points will be summarized using number (%) of events at each time point and analyzed using a generalized estimating equation (GEE) model, in which treatment, time, interaction between treatment and time as fixed effects, HIE (presence or absence) and seizure burden (high or low) as covariates,

CONFIDENTIAL

and participant as cluster effect. Exchangeable covariance structure will be used. The RR together with their 95%CIs at each time point will be derived.

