7.2.2. Analysis of continuous outcomes

The continuous variables such as biochemical markers will be summarised using number of subjects (n), mean, standard deviation (SD), median (IQR), minimum, and maximum by treatment group, and will be analysed by a GLM model with treatment as a study variable, HIE (presence or absence) and seizure burden (high or low) as covariates, and with normal distribution and identity link function. Differences in mean outcomes with their two-sided 95% CIs between two groups will be derived from the GLM model.

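### The only log-rank/Cox specification for the time-to-treatment endpoints uses treatment arm alone; adding the SAP's two factors (HIE, seizure burden) is a small gain at almost no cost

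*Protocol*

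**What the plan says.** Protocol 9.4.3 gives the only survival methods in either document: "the Kaplan-Meier curves will be presented and compared by the log rank test by treatment group", and the "hazard ratio and its 95% confidence interval will be calculated using Cox regression model with the treatment arm as the study variable". It names no strata or covariates.

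SAP 3.7.2 lists three interval endpoints: first to second phenobarbital dose, second dose to alternative anticonvulsant, and first dose to alternative anticonvulsant. SAP 7.2 has subsections for binary and continuous outcomes only. Protocol 9.4.1 sends the reader to the SAP for specifics, so nothing replaces or completes the protocol sentence.

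SAP 5.3 has a heading for stratification factors with two entries, "Presence or absence of HIE" and "High or low seizure burden". Both enter the primary model (SAP 7.1.1) and the repeated-binary GEE (SAP 7.2.1: "interaction between treatment and time as fixed effects, HIE (presence or absence) and seizure burden (high or low) as covariates"). They also enter the continuous model (SAP 7.2.2: "HIE (presence or absence) and seizure burden (high or low) as covariates, and with normal distribution and identity link function"). Single-measurement binary outcomes are to be handled much as the primary endpoint is.

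Protocol 6.3 and SAP 3.4 describe randomisation through the IWRS, and SAP 3.4 adds permuted blocks. Neither names strata. SAP 5.6 calls secondary analyses exploratory.

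**The concern.** The SAP treats HIE and seizure burden as important enough for its other efficacy models, but the time-to-treatment endpoints are left with an arm-only test. If the two factors predict the need for further treatment, an analysis that ignores them has less power than one that uses them, although the plan already requires both for other models. If randomisation is also balanced on them, an unstratified test rejects less often than its nominal level under the null.

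The SAP is also silent on the method for these endpoints. An analyst could follow the protocol (arm only) or apply the SAP's general pattern (two factors). The choice between an unadjusted and an adjusted hazard ratio could then be made after results are seen.

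**Working it through.** **1. The plan's own figure.** Inputs are 70% versus 50% control, alpha 0.05 (two-sided reproduces) and 80% power (protocol 9.2, SAP 3.6). With pooled variance under the null:

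n = [1.96·√(2·0.6·0.4) + 0.8416·√(0.7·0.3 + 0.5·0.5)]² / 0.2² = (1.358 + 0.571)² / 0.04 ≈ 93 per group.

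186 / 0.95 = 195.8, so 196 are randomised, 98 per arm. This reproduces the plan. The documents state no event count or power for the time-to-event endpoints, so the rest is illustration.

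**2. Translation to a time scale.** The planning rates imply that 50% (low dose) and 30% (high dose) need further treatment by 24 h. With exponential times:

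- HR = ln(0.7) / ln(0.5) = 0.515, so |ln HR| = 0.664.
- Events = 98·0.5 + 98·0.3 = 78.4.
- Schoenfeld power = Φ(√78.4/2 · 0.664 − 1.96) = Φ(0.98) ≈ 84%.

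**3. Simulation with the marginal 24-h rates held at 50% and 30%.** Exponential times are censored at 24 h, with 98 per arm and two-sided 5% Wald tests. Assumptions not in the documents: 60% HIE, 50% high burden, prognostic hazard ratios of 1.5-2 for HIE and 2-3 for burden.

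| Quantity | Arm only | Adjusted or stratified |
|---|---|---|
| Power, factors prognostic | 83-85% | 85-90% |
| Power, factors not prognostic | 82.7% | 82.8% |
| Null rejection, randomisation stratified | about 3.0-4.5% | close to 5% |
| Null rejection, randomisation not stratified | about 5% | about 5% |

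Within a setting the power difference is about 2-6 points. With 2,000 runs, the Monte Carlo standard error near 85% is √(0.85·0.15/2000) = 0.8 points.

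**4. Where the gain comes from.** In these runs the mean standard error of the log hazard ratio was 0.235-0.236 arm-only and 0.236-0.238 adjusted, so it did not fall. The mean log hazard ratio moved from about −0.67 to between −0.70 and −0.75. A Wald approximation gives the same picture:

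- Arm only: 0.67/0.235 = 2.85; Φ(2.85 − 1.96) ≈ 81%.
- Adjusted, weaker factors: 0.70/0.236 = 2.97; Φ(1.01) ≈ 84%.
- Adjusted, stronger factors: 0.75/0.238 = 3.15; Φ(1.19) ≈ 88%.

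The hazard ratio goes from exp(−0.67) = 0.51 to between exp(−0.70) = 0.50 and exp(−0.75) = 0.47. This is the usual gap between a marginal and a conditional hazard ratio.

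**5. A second calibration.** Here the conditional hazard ratio is held at 0.515, both factors have the same prognostic hazard ratio, arms are balanced within the four strata, and each setting has 3,000 runs.

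| Prognostic HR per factor | Log-rank power: arm only / stratified | Mean HR: arm only / stratified | Null rejection: arm only / stratified |
|---|---|---|---|
| 1.0 | 83% / 83% | 0.51 / 0.51 | 4.6% / 4.7% |
| 1.5 | 82% / 83% | 0.52 / 0.51 | 4.6% / 5.0% |
| 2 | 80% / 83% | 0.53 / 0.51 | 3.4% / 5.1% |
| 3 | 77% / 85% | 0.55 / 0.51 | 2.7% / 4.7% |

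The direction is the same. The 8-point gap in the last row needs both factors to triple the hazard, which is outside the range in step 3.

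**6. Which endpoints this describes.** The simulated event is the first need for further treatment within 24 h, which is closest to time to second dose. First dose to alternative anticonvulsant is a different event, but it starts at randomised treatment and the same reasoning applies. Second dose to alternative treatment exists only in neonates given a second dose: at planning rates at most about 98·0.5 = 49 and 98·0.3 ≈ 29. That subset is selected after randomisation, and stratifying by baseline factors does not restore a randomised comparison.

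**The case against.** The arm-only analysis can be defended. The log-rank test is valid with or without stratified randomisation, and a marginal hazard ratio is a legitimate target. Protocol 9.4.2 also describes its primary model with treatment alone, and the SAP later added the two factors to it. The Cox sentence may therefore be an outline that was never updated, not a decision to exclude them. The endpoints are exploratory, no power is claimed for them, and the size of the loss rests on assumed prevalences and hazard ratios. All of this stands, and it limits the severity.

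It also rules out some stronger readings that a reader might infer:

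- That the test as written has a type I error below nominal. This needs stratified randomisation. The only support is a heading in SAP 5.3; the two randomisation sections name no strata.
- That adjustment buys precision. In these Cox models the standard error did not fall.
- That the hazard ratio would otherwise fail to match the adjusted estimates beside it. It is on a different scale from risk differences, risk ratios and mean differences whatever the covariates.
- That all three intervals are repaired by stratifying. The interval from second dose to alternative treatment is not.

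The objection does not remove the remaining point. The SAP already requires both factors in its other efficacy models, using them here costs essentially nothing if they are not prognostic, and a SAP paragraph for these endpoints is needed in any case.

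**Conclusion.** The point holds as a low-severity improvement. The plan's only log-rank/Cox specification omits two factors that the SAP uses in its primary, repeated-binary and continuous models. The planned test is not invalid and does not inflate type I error.

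The cost is about 2-6 points of power for prognostic hazard ratios of 1.5-2 (HIE) and 2-3 (burden), and nothing material if the factors are not prognostic. These figures assume 60% HIE, 50% high burden, exponential times and the planning rates; the documents give neither the prevalences nor the prognostic strengths. Conservatism (null rejection about 3.0-4.5%) follows only if randomisation is in fact stratified, which the documents leave open. The conclusion applies to the two intervals that start at the first dose.

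**What to change.** Add a time-to-event paragraph to SAP 7.2 and bring protocol 9.4.3 into line:

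- Analyse first dose to second dose, and first dose to alternative anticonvulsant, by a log-rank test stratified by HIE and high/low seizure burden. Take the hazard ratio from a Cox model adjusted for, or stratified by, both factors, and name one of the two forms in advance.
- Keep the arm-only log-rank test and Cox model as a sensitivity analysis.
- State the high/low burden cut-off, use the same one in the SAP's other models, and fix it before unblinding. At present no cut-off is given for this factor; the median split in SAP 5.4 is for subgroups only.
- State in protocol 6.3 and SAP 3.4 whether randomisation was stratified and, if so, by what.
- Present second dose to alternative treatment descriptively, because it is defined only in neonates who needed a second dose.

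The cost is a short text change and a STRATA or covariate statement in the program, with no new data or participants. The downside is that the main hazard ratio becomes conditional on the two factors; the report should say so and show the arm-only estimate beside it.
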